- Describe the criteria that define who will be included or excluded in your final study sample.

Aim 1: The final study sample will include 200 women randomized into 1 of 2 arms: Intervention (MomZing, n=100) or Control (Usual Care, n=100).

Women will be considered eligible if they:

- Are English-speaking and between the ages of 18 and 45
- Had prenatal care at KPNC and delivered their child at a KPNC hospital
- Are at increased risk of PPD between 2 and 6 months postpartuma
- Own a smartphone, computer, or TV with internet access
- Do not have a depression diagnosis or receive any treatment for depression (e.g. taken antidepressant medications or received psychotherapy)
- Are free of a heart condition and a physician recommending medically supervised physical activity
- Do not have chest pain during physical activity, or developed chest pain within the prior month
- Do not take medication for hypertension or a heart condition
- Have no tendency to fall due to syncope or dizziness
- Have no orthopedic problems that might be aggravated by physical activity
- Do not have exercise-induced asthma
- Are not pregnant or planning to become pregnant in the ensuing three months

- Have a Body Mass Index (BMI) between 18.5 and 40 (kg/m^2)
- Are not engaging in regular, moderate-to-vigorous physical activity >30 minutes per week

and if their infantsb:

- Are between 2 and 6 months old
- Weigh between 11-22 pounds
- Are free of chronic illness/disorder that prevents someone from holding or lifting them

aWomen will be considered at increased risk for PPD if they do not have a current depression diagnosis defined as a diagnosis between delivery and the time of the PHQ-9 score but have a PHQ-9 score between 10-19. Women who have a PHQ-2 score of  $\geq 3$ , administered at well-baby visits, will also be considered at increased risk.

bThe mothers in the intervention will be instructed how to safely exercise based on the infants' weight and developmental stage.

Aim 2: All clinicians and clinical leaders who are identified through the OBGYN Peripartum Depression Champions Committee, which consists of a depression champion clinician from different KPNC facilities, will be eligible to participate in the qualitative interviews.

- Describe how individuals will be screened for eligibility.

Please see above for eligibility requirements.

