**9. Study Procedures**

## a. Description

Describe and explain the study design, including:

- A detailed chronological description of all research procedures.

This is a hybrid effectiveness-implementation study including 1) a randomized controlled trial to test the effectiveness of MomZing to increase physical activity and reduce postpartum depressive symptoms in women at increased risk of PPD and 2) evaluation of implementation of MomZing within the KPNC health care delivery system. We will identify potential participants and assess them through clinician referrals and using KPNC's electronic health records data for eligibility. All eligible and recruited women will complete a baseline survey including self-report of PA and wear a research-grade accelerometer for 7 continuous days to assess baseline PA. We will mail the accelerometer and wearing instructions, and also provide a self-addressed prepaid postage envelope for participants to return the items after each measurement period. All participants will be informed that they do not have to answer any question in the surveys they do not wish to answer. We will then randomize 200 women into 1 of 2 arms: 1) Intervention (MomZing, n=100) or 2) Control (Usual care, n=100) using a restricted randomization scheme to ensure an acceptable level of between-arm balance in the distribution of important covariates (e.g. KP clinic, race/ethnicity, age, parity, marital status, and education). The nature of the group assignment and intervention does not allow for blinding of the treatment conditions from the participant or the research assistant whose task is to register and explain the use of the MomZing intervention. The programmer/analyst, biostatistician, and investigators will be blinded to the study arms. Once randomized, participants will begin their assigned group's intervention or control treatment for 3 months. We will obtain both self-report and accelerometer-measured PA and depressive symptoms at 3 months (T1) and 6 months (T2) post-baseline for each woman in their respective arms. There will be one final survey when the participant's child is 12 months old to assess child development. Non-respondent data will be used for those who do not respond to the recruitment emails and calls. They will be given 30 days to opt out of the study and informed that their data may be used if they do not respond.

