- What information and/or biospecimens will be collected including during long-term follow-up.

*Please note, if biospecimens being collected are being used to develop an investigational in vitro diagnostic device, an IDE for the device may be needed. Please review the IVD Device FAQs in IRBNet for guidance.*

**Data Sources:** Data used in this study will be from a combination of EHR databases, surveys, accelerometers, and the MomZing website. We will conduct surveys via REDcap and accelerometer-measured PA data collection at 3 timepoints: a) baseline (T0, before intervention), b) 3 months post-baseline (T1), and c) 6 months post-baseline (T2). There will be one final survey to assess 12-month child development as well. Lastly, we will conduct qualitative interviews with key stakeholders to evaluate procedures for implementation.

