**Statistical Analysis:**

Primary analyses will include estimation of mean minutes of moderate/vigorous physical activity and mean PHQ-8 depression screening score at each point in time stratified by treatment arm. Patterns in the group differences across time will be noted, and the results of these time-stratified analyses will be synthesized via linear regression models with parameter estimation via generalized estimating equations (GEE) for each outcome separately. GEE accommodates the within-patient correlation in repeated measures to obtain valid estimates of intervention effects and associated standard errors. In addition to study arm and time (categorical variable), model covariates will include those used in the randomization procedure (KP clinic, race/ethnicity, age, parity, marital status, education). In addition, this a priori specified set of model covariates will include baseline depression score and household income as main effects in regression models given their strong association with the outcome; inclusion of such covariates can improve statistical power and precision. Heterogeneity in effect by time since baseline will be assessed by including a treatment by time interaction term.

The approach to analysis of additional continuous outcomes (sleep, stress, anxiety symptoms, maternal infant bonding, infant development) will utilize multivariable linear regression analysis, with the approach to estimation (GEE), inclusion of model covariates, and examining of heterogeneity in treatment effect over time as described above.

The approach to analysis of additional categorical outcomes (meeting PA guidelines, depression diagnosis, anxiety diagnosis) will utilize multivariable log-binomial regression analysis, with the approach to estimation (GEE), inclusion of model covariates, and

examining of heterogeneity in treatment effect over time as described above. We propose the log binomial regression model for point and interval estimation of relative risks (ratio of proportions) rather than the logistic regression model for estimation of odds ratios, for ease in interpretation and avoidance of odds ratio misinterpretation given the relatively high expected frequency of these outcomes.

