Sensitivity analyses will examine inclusion of additional covariates in our estimation of treatment effect, with a focus on variables with chance imbalance in distributions by treatment group (determined in preliminary analyses). Analyses resulting in an appreciable change in the estimate of treatment differences or increase in the precision of the treatment effect will be noted.

- When applicable, the power analysis.

We will recruit 200 women (100 per group). For depressive symptoms, the minimum-detectable difference between groups is in the “small” to “medium” effect range of .43 standard deviation units (two-sided test,  $\alpha=.05$ ). For analyses of meeting PA guidelines, we will have sufficient power (.80) to detect a 20 point difference as based on the literature between the MomZing intervention (43%) and control group (23%), allowing for up to a 16% loss-to-follow-up (which is similar to that of previous lifestyle intervention studies at KPNC).

- Any procedures that will be used for quality control of collected data.

The programmer and study investigators will follow standard data management procedures to ensure the quality of the data. The programmer will draw from shared resources of the programmer group, which include detailed documentation about data sources and characteristics, shared programming code to prepare datasets according to standardized parameters, and consultation with other programmers to ascertain best practices based on procedures developed in earlier projects. There will be systematic data checks by assessing the presence of outliers and missing values and calculating the distributions of variables over time periods, medical facilities, demographic subgroups, and other categories. The study team will also compare these results to expectations based on other comparison data or studies, and further investigate possible reasons for any data anomalies. They will develop procedures to address data irregularities, such as by cleaning the data, augmenting the data with other relevant variables, or using analytic techniques to reduce as much as possible the impact of bias in the data.

c. Sharing of Results with Subjects

Describe whether results (study results or individual subject results, such as results of standard or research lab tests and genetic tests) will be shared with subjects or their providers and under which circumstances.

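### The primary MVPA model leaves out baseline MVPA and does not say what role T0 plays, so it gives up precision that the collected data would supply

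*Combined protocol and SAP*

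**What the plan says.** Section 9b, Statistical Analysis, sets the two primary outcomes together: "Primary analyses will include estimation of mean minutes of moderate/vigorous physical activity and mean PHQ-8 depression screening score at each point in time", by arm. Each is then modelled by linear regression with GEE. The terms are given once for both: "In addition to study arm and time (categorical variable), model covariates will include those used in the randomization procedure" (clinic, race/ethnicity, age, parity, marital status, education), and "this a priori specified set of model covariates will include baseline depression score and household income as main effects in regression models". The stated reason for the added covariates is their association with the outcome and the resulting gain in power and precision. On the interaction: "Heterogeneity in effect by time since baseline will be assessed by including a treatment by time interaction term".

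Section 9a has all recruited women "wear a research-grade accelerometer for 7 continuous days to assess baseline PA", and randomization follows. Accelerometry is repeated at T1 (3 months) and T2 (6 months).

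Section 9b also provides that "Sensitivity analyses will examine inclusion of additional covariates in our estimation of treatment effect", chiefly for variables found to be imbalanced by chance.

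**The concern.** The PHQ-8 model contains the baseline value of its own outcome; the MVPA model does not. By the plan's own rationale for covariates, baseline MVPA is an obvious candidate, and it is already being collected.

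The role of T0 is also open. The primary estimates at each time point could include T0, while the use of baseline depression as a covariate suggests that only T1 and T2 are outcomes. Three readings are possible for MVPA:

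- **Follow-up only.** T1 and T2 are the outcome rows, and baseline MVPA is unused.
- **Change from T0.** T0 is an outcome row, and the arm-by-time term gives the T1 and T2 contrasts against T0.
- **Pooled arm effect.** T0 is an outcome row, and one arm effect is reported from the main-effects model.

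The first two are the likely ones. They are unbiased but waste information to different degrees. The third averages in a visit at which the true difference is zero. It is less natural, because the PHQ-8 baseline would then be both outcome and covariate. That argument applies equally to change from T0, however, and not directly to MVPA, so the wording alone does not rule the third reading out. Until T0's role is fixed, the primary contrast is not settled before the data are seen.

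**Working it through.** **Inputs.** 100 women per arm, two-sided alpha 0.05, power 0.80 (stated for the activity-guideline comparison) and loss up to 16%, all from the power analysis in section 9b. This leaves 100 × 0.84 = 84 per arm. The correlation rho among T0, T1 and T2 after the listed covariates is not in the documents. It is assumed equal for all pairs and varied. The entry rule "Are not engaging in regular, moderate-to-vigorous physical activity >30 minutes per week" (section 5b) may narrow the baseline range and lower rho, so 0.2 is included. The outcome SD is set to 1.

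**The plan's own figures.** Detectable difference at 84 per arm: 2.80 × sqrt(2/84) = 0.432 SD, matching the stated 0.43 for depressive symptoms. Power for 43% versus 23% at 84 per arm, with pooled variance under the null: (0.20 − 1.96 × 0.0726)/0.0709 = 0.815, giving 0.79, in line with the stated 0.80. The plan gives no target for mean MVPA.

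**Variance per woman of the T1/T2 average contrast.**

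- Follow-up only: (1 + rho)/2
- Change from T0: (1 + rho)/2 + 1 − 2·rho
- T1/T2 with baseline MVPA as covariate: (1 + rho)/2 − rho²

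SE = sqrt(2 × variance/84). Detectable difference at 80% power = 2.80 × SE.

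| rho | Variance: follow-up only / change / adjusted | Cut vs follow-up only | Cut vs change | Detectable difference (SD), same order |
|---|---|---|---|---|
| 0.2 | 0.60 / 1.20 / 0.56 | 7% | 53% | 0.33 / 0.47 / 0.32 |
| 0.3 | 0.65 / 1.05 / 0.56 | 14% | 47% | 0.35 / 0.44 / 0.32 |
| 0.5 | 0.75 / 0.75 / 0.50 | 33% | 33% | 0.37 / 0.37 / 0.31 |
| 0.7 | 0.85 / 0.45 / 0.36 | 58% | 20% | 0.40 / 0.29 / 0.26 |

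If the T1–T2 correlation is instead fixed at 0.7, the variances are 0.85 and 0.85 − rho², and the cut against follow-up only is 5%, 11%, 29% and 58%.

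**Power at 0.43 SD, rho 0.5.** Power = Phi(0.43/SE − 1.96). Follow-up only or change: SE = sqrt(2 × 0.75/84) = 0.134, power 90%. Adjusted: SE = sqrt(2 × 0.50/84) = 0.109, power 98%. The 0.43 is borrowed from the depressive-symptom statement.

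**Single visit.** The variance factors are 1, 2(1 − rho) and 1 − rho². The cut against follow-up only is rho²: 4%, 9%, 25%, 49%. Against change from T0 it is (1 − rho)/2: 40%, 35%, 25%, 15%. Power at 0.43 SD and rho 0.5 is 80% for either reading and 90% with adjustment.

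**Bias check.** In simulation with a true effect of 0.43 at T1 and T2 (6,000 runs per rho), the mean estimate was 0.43 for follow-up only, change from T0 and the adjusted model. For the pooled arm effect it was 0.285, against the expected (0 + 0.43 + 0.43)/3 = 0.287. A separate GEE simulation with exchangeable working correlation (rho 0.3, 0.5 and 0.7, 400 runs each) gave 0.42 to 0.43 for the first three and 0.28 to 0.29 for the pooled effect.

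**The case against.** The strongest reply is that this is a matter of efficiency and its size is unknown. Rho is not in the documents and the entry limit may lower it. At rho 0.2 the detectable difference moves only from 0.33 to 0.32 SD against follow-up only. No stated power figure fails, since both reproduce without baseline adjustment. All of that stands.

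The larger percentages are for the T1/T2 average, a contrast that the plan does not name, and the single-visit gains are smaller. This also stands, and both sets are shown above. The average is, however, what the arm term of the stated main-effects model estimates when T1 and T2 are the outcome rows.

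The sensitivity analyses would note any gain in precision from added covariates. This is partial cover: baseline MVPA is not named, the focus is on imbalance seen in the data, and the primary estimate is unchanged. Blinding of the biostatistician and investigators limits choosing a model by its result, but it does not recover lost precision or fix the contrast.

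Finally, keeping T0 as an outcome row with the arm means constrained equal at T0 is a sound alternative to covariate adjustment. That is a choice between remedies, and the plan specifies neither.

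**Conclusion.** The concern holds and should be fixed. The prespecified list omits baseline MVPA and T0's role is not stated. For any rho strictly between 0 and 1, adjustment beats both likely readings. Follow-up only loses most when rho is high and change from T0 loses most when rho is low, so neither is safe across the range. The gain in variance of the T1/T2 average runs from 7% to 58% against follow-up only and from 53% to 20% against change from T0 as rho goes from 0.2 to 0.7.

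These sizes rest on 84 per arm, the assumed correlations and a normal approximation. The statement that the likely readings are unbiased also assumes that loss to follow-up does not depend on baseline MVPA differently by arm. Real bias, with the estimate at two thirds of the truth, arises only under the less likely pooled reading, but one sentence in the plan would exclude it.

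**What to change.** In section 9b:

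1. State that T1 and T2 are the outcome rows and that T0 is baseline only.
2. Add T0 accelerometer MVPA to the covariates of the MVPA model, and keep baseline PHQ-8 in the PHQ-8 model. If self-reported minutes are analysed, use the self-reported T0 value there.
3. Name the primary contrast: the arm difference at T1 and at T2 from the arm-by-time term, or their average.
4. In the secondary continuous models, add the outcome's own T0 value only where it is measured at T0. This excludes infant development, which is surveyed at 12 months.

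A short statement on handling missing T0 accelerometry would complete it. The core change is two or three sentences of analysis-plan wording. It needs no new MVPA data, because T0 accelerometry is already scheduled for every woman.

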#### 10. Privacy, Confidentiality and Data Security

Describe the steps that will be taken to protect subjects' privacy during recruitment, consent and study procedures.

All data collected as part of this study will be held in strict confidence. Only study staff will have access to the data collected as part of the study, and no identifying information will be used in any reported findings, thus ensuring that participants feel comfortable and that there is reasonable privacy.

Data collected during recruitment/screening or when a potential subject is contacted for the survey but declines participation will be destroyed at the end of the study. Subjects will not be contacted about participation after they have declined.

Describe the plan for storage of data and/or biospecimens including:

- Who will have access and how.

The PI, Co-I's, and study team will all have access to identifiable information from the medical record and other clinical databases described above.

- Where the data/materials will be stored and for how long. Indicate if data will be encrypted and password protected and if transportable/removable media will be used.

PHI will be stored in password protected or encrypted electronic files and stored on protected KPNC servers within the KP network secured by firewalls. Passwords will not be disclosed to any party not involved in the study. Patient identifiers will not appear in any part of the publications. When it is necessary to share PHI information among study parties within KPNC, we will transmit the files (password-protected/encrypted) through encrypted email or secure file transfer. The information will be stored for the length of the project and destroyed after the final manuscripts are published.

- If applicable, how will data be transmitted?

The data will be transmitted using the KP NCAL secure file transfer system.

- What identifiers will be included.

Names and other identifying information on study subjects such as dates, postal addresses, phone numbers, email addresses, and medical record numbers will be included.

- Any other steps that will be taken to ensure security (e.g., training of staff, authorization of access, password protection, encryption, physical security, and separation of identifiers from data and specimens, certificates of confidentiality).

To ensure security we will properly train staff and restrict access to data only to the study team. As such, we believe our plan to protect the data is appropriately mitigated.

- Describe the plan to destroy/archive or retain data at the end of the study. If storing information and/or identifiable biospecimens for future research, complete the next section.

Personal identifiers associated with participants will be destroyed as soon as possible after the study has finished and all manuscripts have been published. Since manuscript submission and revision process often requires re-access of patient information, patient identifiers will be kept until all publications generated from the study have been finished, at which time all patient identifiers will be destroyed at the close of the study.

#### 11. Information and/or Biospecimen Banking for Future Research

If you are creating a repository, please submit a separate protocol.

Indicate if biospecimens may be used for future research and whether that may include genetic research.

N/A

State if information or biospecimens will be sent to a separate repository. If data or specimens will be banked in a repository for future use as part of this protocol submission address the following questions:

- What will be banked and what identifiers will be associated with the information or biospecimens?

N/A

- Where and how will the information or specimens be stored?

N/A

- For what purpose will the information or specimens be used? Include a general description of the types of research that may be conducted with the identifiable private information/biospecimens (e.g. research on cancer).

N/A

- How will the information or specimens be accessed, and who will have access?

N/A

- Describe the procedures to release information or specimens, including the process to request a release, approvals required for release, who can obtain information or specimens, and the information to be provided with specimens.

N/A

- How long will identifiable private information/biospecimens be stored?

N/A

## 12. Collection of data from subjects electronically

If you will collect any data from participants electronically (including email, website, etc.), explain:

- Does the study involve a Mobile Device or Application. If yes, please indicate the source/manufacturer/developer of the product:

The consent and patient surveys will be developed in REDcap. The intervention arm also includes the MomZing website, which can be accessed using any internet-enabled device and automatically records adherence data (time, type, date, duration of exercise video) for each participant. Quarterly usage reports for participants in the intervention will be generated and sent to us by Klein Buendel (KB), who will only receive study IDs, assigned to each participant upon enrollment in the intervention. KB is a behavioral health communications firm specializing in the development of programs to educate communities about health issues. KB and its role in the study has already been reviewed and approved by TRO (see Appendix V).

Interviews with the clinicians will be conducted in-person, by telephone or video (via Microsoft Teams), whichever is more convenient for them.

- How and what data will be collected. Indicate if PHI is collected electronically (including via an app) and if there is any interface with the subject's personal accounts (for example: if subjects need to create an account to use the device, or if the device interfaces with an external source of data, or medical record).

**Patient surveys:** Information on physical activity, demographic characteristics and other factors including questionnaires to assess social support, depressive symptoms, stress, sleep quality and others, will be ascertained in the surveys. PHI (phone, mailing address, and email) will be collected electronically. Participants will not need to create any accounts to access REDcap. Once they click the provided link, they will go directly to the platform.

**MomZing:** The MomZing website will record adherence data and Klein Buendel will send usage reports using study IDs, assigned and provided by us, only. PHI will not be collected electronically. Participants in the intervention will not need to create any accounts to access the website. Accounts will already be set-up by the study team. Once a participant enrolls and is randomized to the intervention arm, she will be given the account information (user and password) to log-in and begin the program.

- How the information will be secured/transmitted/stored (encryption, password protection, etc.; may require consultation with IT department). Include a data flow diagram if data will flow through multiple parties (such as a hosting provider or coordinating center).

Data will be stored on protected KPNC servers within the KP network secured by firewalls and monitored by the IT department. When it is necessary to share data among study parties within KPNC, we will transmit the files (password-protected/encrypted) through encrypted email or secure file transfer. The information will be stored for the length of the project and destroyed after the study is complete.

Data (no PHI) will be stored on the Momzing website, maintained by Klein Buendel, using a Secure Sockets Layer (SSL) protocol. When they send the adherence data (password protected .csv files), they will use encrypted email or secure file transfer. The information will be stored on protected KPNC servers for the length of the project and destroyed after the study is complete.

- Any risks to the participants' privacy posed by using these methods (describe in consent, as applicable).

No, there will be no risks to participants' privacy; we believe our plan to protect their privacy is appropriately mitigated.

- Describe if email containing PHI will be used to communicate with participants? (Per KP policy, securing messaging must be used for all communications containing PHI.)

No email messaging containing PHI will be used to communicate with participants.

- How you will verify the participant's identity.

Participants: We will use the email on file in KP.org for each participant. Using REDcap, we will create a study ID and unique survey link for each woman and attach in each recruitment email. She will also need to provide her own unique credentials (date of birth), thus authenticating her identity. For participants who are recruited initially by phone, she will not need to provide her date of birth as her identity will be confirmed by the research assistant.

Clinicians: we will only use their KP-issued work email to send the recruitment emails.

